5.1.2.3. Follow Up Relative Day

Follow Up (FU) start date (FU Day 1) is defined in [Table 3](#). Efficacy and safety assessments during the FU phase will be assigned a day relative to this date. The FU study day in the FU phase (ADY) is defined as:

$$FU\ ADY = \text{visit date} - FU\ \text{start date} + 1$$

for visits on or after FU Day 1.

5.1.3. Visit Windows

As participants do not always adhere to the protocol visit schedule, the following rules are applied to assign actual visits to analysis visits. All visits for all assessments (safety, efficacy or PK) will

be uniquely allocated within each phase to an analysis time point based on the analysis relative day (ADY) compared with the target day based on Table 4. All assignments will be made in chronological order. Once a visit date is assigned to a visit window, it will no longer be used for a later time point except for the end of treatment period 1 (EOT1), end of treatment period 2 (EOT2), and end of study (EOS) visits. If a participant has 2 or more actual visits in one visit window, the visit closest to the target day will be used as the protocol visit for that visit window. The other additional visit(s) will not be used in the summaries or analyses, but they can be used for determination of clinically important endpoints. If 2 actual visits are equidistant from the target day within a visit window, the later visit is used. If there are two or more measurements on the same day, then the last measurement in chronological order will be used. If the time of the assessment is not available, the highest record/sequence number will be selected.

The listings will include all measurements, also those multiple assessments with the same visit window/phase. Spaghetti plots will also display all measurements.

End of treatment period 1 (i.e. EOT1), end of treatment period 2 (i.e. EOT2) and end of study (i.e. EOS) time points will be included in all analyses over time unless stated otherwise.

Table 4 provides the analysis time points and time intervals for each visit per analysis phase.

Table 4: Visit Windows

a) Screening, Treatment Period 1, and Treatment Period 2

Analysis phase	Target day	Analysis time point (Week)	Analysis time point (label)	Time interval (days)
Screening	$-\infty$	-1	Screening	<0
Treatment period 1	1	0	Baseline	Pre-dose: 1
	15	2	Week 2	[2,22]
	29	4	Week 4	[23,43]
	57	8	Week 8	[44,81]
	85 ^a	12.1	Week 12 period 1	[82, 92] ^a
	Last visit in treatment period 1	12.15 ^b	EOT1 ^b	
Treatment period 2	85 ^a	12.2	Week 12 period 2	[82, 92] ^a
	99	14	Week 14	[93,106]
	113	16	Week 16	[107,127]
	141	20	Week 20	[128,155]
	169	24	Week 24	[156,183]
	Last visit in treatment period 2	25 ^c	EOT2 ^c	

^a Day 85 is the target day for the first administration of PegIFN- α 2a. Time interval [82-92] was selected to align the visit window with the protocol Schedule of Activities for Week 12. Any assessments performed before the administration of PegIFN- α 2a (date/time) at week 12 will be considered under treatment period 1 (Week 12 period 1) and assessments after the administration of PegIFN- α 2a (date/time) will be considered as treatment period 2 (Week 12 period 2).

^b End of treatment period 1 (EOT1) visit will be the last visit of treatment period 1.

^c End of treatment period 2 (EOT2) visit will be the last visit of treatment period 2.

b) Follow-up

Analysis phase	FU Target day	Analysis time point (Week)	Analysis time point (label)	Time interval (FU days)
Follow-up	15	26	Follow-up Week 2	[1, 22]
	29	28	Follow-up Week 4	[23, 43]
	57	32	Follow-up Week 8	[44, 71]
	85	36	Follow-up Week 12	[72, 99]
	113	40	Follow-up Week 16	[100, 127]
	141	44	Follow-up Week 20	[128, 155]
	169	48	Follow-up Week 24	[156, 183]
	197	52	Follow-up Week 28	[184,211]
	225	56	Follow-up Week 32	[212, 239]
	253	60	Follow-up Week 36	[240, 267]
	281	64	Follow-up Week 40	[268, 295]
	309	68	Follow-up Week 44	[296,323]
	337	72	Follow-up Week 48	[324, +∞]
	last visit in the study	999 ^a	EOS ^a	

^a End of study (EOS) visit (last available data during the follow-up phase) will be the last visit in the study.

5.1.4. Baseline

In general, the baseline assessment is defined as the last observed non-missing measurement before the date and time of the first administration of any of study agents.

In case the first administration measurement time is missing, the first observed measurement on TP1 Day 1 will be used as the baseline measurement. If no observed measurement on Day 1, the last observed measurement before Day 1 will be used as the baseline assessment.

5.1.5. Additional Reference Timepoint

An additional reference timepoint (RT) will be used for an additional analysis of selected efficacy endpoints for treatment period 2 and FU phase.

The RT for those analyses is defined as the last observed non-missing measurement before the first PegIFN- α 2a intake.

5.1.6. Analysis Specifications

In general, continuous variables will be summarized using descriptive statistics including the number of participants, mean, standard deviation (SD), two-sided 90% confidence interval (CI), median, and range. The 90% CI for continuous endpoints is constructed using the t-distribution. Binary or categorical variables will be summarized using the number and percentage of participants in each category and 90% CI using Clopper-Pearson exact method for the single sample proportion (Newcombe 1998). For time-to-event variables, using the Kaplan-Meier approach, a summary table including number of participants included in the analysis, number of participants censored, 25th and 75th percentiles, median time-to event and 90% CI will be shown. Graphic displays will also be used to summarize the data.

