5.1.7. Level of Significance

Due to exploratory nature of this study, no formal test will be performed. Only two-sided 90% CIs will be provided with no adjustment for multiplicity.

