5.4.2.2. Continuous Endpoints

5.4.2.2.1. HBsAg, HBeAg, HBV DNA and ALT

Descriptive statistics on actual values [original unit and \log_{10} transformed values (except for ALT)], changes from baseline and changes from RT over time in HBsAg, HBeAg, HBV DNA and ALT will be summarized. Mean (+/- SE) plots of the values, change from baseline and change from RT over time will be presented by analysis phase. The change from baseline value to nadir (i.e. maximum decrease for each participant) in HBsAg, HBeAg and HBV DNA will be summarized descriptively. Box plots of the changes to nadir in HBsAg, HBeAg, and HBV DNA will display the distribution.

Change from baseline based on \log_{10} transform for quantitative HBsAg and HBeAg will be analyzed using mixed effects model for repeated measures [MMRM]) including analysis time point (week), baseline blood marker variable, and their interaction. The covariance structure will include a random intercept at the level of the participant to capture between-participant variability, while within-participant variability will be captured with an unstructured (type=UN) covariance matrix. In case of convergence problems, simpler variance-covariance structures such as Toeplitz or AR (1) will be considered. The selection of any of these structures will be determined after exploration of the observed correlation structure. The LS mean of change from baseline, standard error (SE), 90% confidence interval (CI) will be provided.

Descriptive statistics on actual values (original unit and \log_{10} transformed values) and changes from baseline (\log_{10} transformed values) at the end of treatment in HBsAg, HBeAg, HBV DNA and ALT (original unit) will be summarized by outcome response (i.e. by achieving a reduction of at least 2 \log_{10} IU/mL in HBsAg levels from baseline to Week 24, by NA treatment completion criteria status), by HBsAg seroclearance at the end of treatment period 2, FU Week 24 and FU Week 48, and by partial cure status at FU Week 24 and FU Week 48, and for participants who achieved functional cure at FU Week 24 and FU Week 48 if there is at least 10% response for each by-group.

Spaghetti plots for both absolute values and changes from baseline of HBsAg and HBV DNA will be presented over time per blood marker by selected subgroups (Section 5.7.5.1).

Waterfall plots for changes from baseline of HBsAg and HBeAg will be presented over time.

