5.5.1.2.3. Anti-HBs Antibodies

Actual values and change from baseline will be evaluated over time when anti-HBs antibodies are assessed.

Change from baseline is defined as the value at a given time point minus baseline value.

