5.5.2.2.3. Anti-HBs Antibodies

The actual values of and changes from baseline in anti-HBs antibodies will be summarized only descriptively in a similar manner as described for values and changes from baseline over time in other blood disease markers in Section 5.4.2.2.1.

For all participants with positive anti-HBs antibodies at baseline who will reach HBsAg seroclearance (as defined in Section 5.4.1.1.4), descriptive statistics will be calculated for the change of anti-HBs antibodies level from baseline at the timepoint when achieving the HBsAg seroclearance. In an additional summary, the change of anti-HBs antibodies level from baseline

at the specific timepoint will be summarized descriptively for the subset of the participants achieving HBsAg seroclearance at any time before or at that given timepoint if there is at least 10% of the participants for the subset.

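### The SAP's t-based 90% CI is not limited to the log10 scale, so original-unit summaries of HBsAg, HBeAg, HBV DNA and possibly anti-HBs get intervals that under-cover when values are strongly skewed

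*SAP*

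**What the plan says.** SAP 5.1.6 sets the default: "In general, continuous variables will be summarized using descriptive statistics including the number of participants, mean, standard deviation (SD"). Also on that list are the 90% CI, the median and the range. A later sentence fixes the method: "The 90% CI for continuous endpoints is constructed using the t-distribution". Neither sentence restricts the scale. SAP 5.1.7 makes these intervals the only inferential output: "Only two-sided 90% CIs will be provided with no adjustment for multiplicity".

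SAP 5.4.2.2.1 applies this to HBsAg, HBeAg and HBV DNA on both scales. Its opening words are "Descriptive statistics on actual values [original unit and". The second scale it names is log10, with ALT excepted. SAP 5.4.1.2.1 makes the changes from baseline and from the additional reference timepoint log10 for HBsAg, HBeAg and HBV DNA. For two of the markers there is also a model of log10 change; its sentence reads in part: "transform for quantitative HBsAg and HBeAg will be analyzed using mixed effects model for repeated measures". Mean (+/- SE) plots of the values and changes are planned, with no scale stated.

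For anti-HBs, SAP 5.5.1.2.3 says: "Actual values and change from baseline will be evaluated over time when anti-HBs antibodies are assessed". SAP 5.5.2.2.3 says these "will be summarized only descriptively in a similar manner as described for values and changes from baseline over time in other blood disease markers". The reference there is to 5.4.2.2.1. Log10 mIU/mL is written out only in the baseline table (Table 12).

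Protocol 9.4.2 asks for 90% CIs with all efficacy summaries. For continuous endpoints it asks for n, mean, SD, median and range.

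**The concern.** Read literally, the two SAP sections together put a symmetric t-interval on the raw-unit mean of each viral marker at each visit. The t-interval relies on the sample mean being roughly normal. With about 50 participants, about 20 HBeAg-positive participants (40% of 50), or a response subgroup of about 5 (the 10% floor in 5.4.2.2.1 applied to 50), that fails when a few values are orders of magnitude above the rest. Off-treatment HBV DNA is the obvious case, because Protocol 6.7.1 sets restart thresholds at 20,000 and 100,000 IU/mL while suppressed participants sit below 60 IU/mL at entry. Such an interval is labelled 90%, usually lies below the true mean when it misses, and can include negative concentrations. These tables would appear at the interim analyses, which SAP 5.8.3.2 says inform internal decisions on further studies.

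**Working it through.** **The plan's own figures.** The documents give no precision figure for a continuous endpoint. Their only CI figures are the Clopper-Pearson intervals in SAP Table 1. All eight reproduce to three decimals (25/50: 0.376 to 0.624; 10/20: 0.302 to 0.698). They are not t-intervals and are not in question.

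**Interval under test.** Mean ± t(0.95, n−1) × SD/√n. The lower limit is negative when SD/mean exceeds √n / t:

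- n=50: 7.071/1.677 = 4.2
- n=20: 4.472/1.729 = 2.6
- n=5: 2.236/2.132 = 1.05

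**Assumption.** No SD or distribution is given for any marker, so lognormal data with log10 SD 0.3 to 1.2 are assumed. Each case uses 20,000 samples. The Monte Carlo standard error is at most √(0.25/20,000) = 0.0035.

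| n | log10 SD | coverage (nominal 0.90) | interval wholly below true mean | interval wholly above | lower limit < 0 |
|---|---|---|---|---|---|
| 50 | 0.3 | 0.88 | 0.10 | 0.02 | 0% |
| 50 | 0.5 | 0.83 | 0.16 | 0.01 | 0.1% |
| 50 | 0.7 | 0.75 | 0.25 | 0.002 | 2% |
| 50 | 1.0 | 0.56 | 0.44 | <0.001 | 16% |
| 50 | 1.2 | 0.44 | 0.56 | <0.001 | 29% |
| 20 | 0.5 | 0.80 | 0.20 | 0.005 | 1% |
| 20 | 1.0 | 0.49 | 0.51 | <0.001 | 33% |
| 5 | 0.5 | 0.73 | 0.26 | 0.003 | 35% |
| 5 | 1.0 | 0.39 | 0.61 | <0.001 | 79% |

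On the log10 scale the same t-interval covers 0.896 to 0.904 in every lognormal case.

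**Cases closer to this trial** (all assumed; n=50 unless stated):

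- *HBV DNA while suppressed.* 60% at 5 IU/mL and 30% at 15 IU/mL (the Table 5 imputations), 10% between 20 and 60: coverage 0.88, never negative.
- *HBV DNA off treatment.* The same, with 5, 10 or 20% rebounding (log10 mean 3.5, SD 1): coverage 0.31, 0.37 and 0.44; lower limit negative in 76%, 76% and 55%.
- *Baseline HBsAg.* Restricted to the entry limit of >100 IU/mL and capped at the assay's upper limit, with log10 mean 3.2 to 3.5 and SD 0.5 to 0.9 before restriction: coverage 0.77 to 0.83, negative in at most 0.3%. At n=20: 0.71 to 0.79, negative in 1 to 13%.
- *Anti-HBs.* 5 to 30% quantifiable (log10 mean 1.5, SD 0.7), the rest at the imputed 2.5 mIU/mL: coverage 0.49 to 0.68, negative in 12 to 22%.

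**One visit by hand.** Take 49 participants at 15 IU/mL HBV DNA and one at 100,000.

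- Mean = (49×15 + 100,000)/50 = 2,014.7.
- With a single outlier, SE = (100,000 − 15)/50 = 1,999.7.
- 90% CI = 2,014.7 ± 1.6766 × 1,999.7 = −1,338 to 5,367.
- Geometric mean = 10^((49 × log10 15 + 5)/50) = 17.9 IU/mL.

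**The case against.** Most of what a reader needs is already planned on the right scale. Log10 values are summarised beside the raw ones, changes are log10, the HBsAg/HBeAg model is on log10 change, and median and range accompany every mean. HBV DNA is also reported by cut-offs and virologic-flare categories, where an outlier would show. The primary endpoint is a proportion with a Clopper-Pearson interval, and nothing is formally tested. All of this stands, and it keeps the point small.

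Several stronger readings are tempting, and the documents do not support them:

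- *Every continuous endpoint is affected.* The 5.1.6 rule is stated as a general default. The safety list (5.6) and the PK list (5.7.1) contain no t-based CI.
- *The error bars on the main efficacy results are wrong.* The log10 set is sound. The planned plots show SE, not 90% CIs, and their scale is unstated, so the coverage figures do not apply to them directly.
- *The markers span the whole assay range.* Table 5 gives quantification limits, not observed spread. Entry requires HBV DNA below 60 IU/mL and HBsAg above 100 IU/mL.
- *Under-coverage is always severe.* No SD is given, and at n=50 with log10 SD 0.3 to 0.5 coverage is 0.83 to 0.88. The hand example above is constructed.
- *Any negative limit is a fault.* It is not one for a change from baseline.
- *Anti-HBs has no log scale at all.* The cross-reference to 5.4.2.2.1 and the baseline table both point to log10; after baseline it is simply not written out.

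Removing the raw-unit mean and SD would go too far, because Protocol 9.4.2 lists them.

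What survives the objection is that a sound log10 interval in the next column does not make the raw-unit interval a 90% interval.

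**Conclusion.** The point holds for original-unit summaries of HBsAg, HBeAg and HBV DNA, and for post-baseline anti-HBs if it is summarised untransformed. For strongly right-skewed values the nominal 90% interval under-covers, with nearly all misses on the low side. The exposure is greatest for off-treatment HBV DNA with rebound (about 0.31 to 0.44 under the assumed 5 to 20%), small response subgroups (0.73 to 0.39 at n=5 for log10 SD 0.5 to 1.0) and anti-HBs (0.49 to 0.68). It is moderate for baseline HBsAg and negligible for suppressed HBV DNA. Every size rests on an assumed distribution. The defect in wording needs no assumption: 5.1.6 sets no scale, and 5.5.1.2.3 and 5.5.2.2.3 name none for anti-HBs. No primary result, log10 summary or model estimate changes.

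**What to change.** - **5.1.6 and 5.4.2.2.1:** state that for HBsAg, HBeAg, HBV DNA and anti-HBs the t-based 90% CI is built only on log10 values and log10 changes. If an interval in original units is wanted, back-transform it and label it a geometric mean with 90% CI.
- **Original-unit summaries of these markers:** omit the CI and keep n, mean, SD, median and range, as Protocol 9.4.2 lists. The log10 interval, or its back-transform, meets that section's request for a 90% CI.
- **Mean (+/- SE) plots of these markers:** specify the log10 scale.
- **5.5.1.2.3 and 5.5.2.2.3:** name log10 values and log10 change for anti-HBs.

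Cost: SAP wording and table shells. Log10 values are already planned for three markers and, at baseline, for anti-HBs. The raw-unit CI column is lost. A geometric mean is a different quantity from the arithmetic mean, so it must be labelled as such.

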5.1.7. Level of Significance

Due to exploratory nature of this study, no formal test will be performed. Only two-sided 90% CIs will be provided with no adjustment for multiplicity.

5.1.8. Missing and Partial Dates Imputation Rules

For analysis and reporting purposes, missing or partial dates in adverse event (AE onset date; AE end date), HBV diagnosis and infection dates, concomitant therapies (start date; end date) will be imputed according to the rules in the following subsections. The original, non-imputed, dates will be used only in listings.

5.1.8.1. Adverse Event Onset Date and Resolution Date

Partial AE onset dates will be imputed as follows:

- If the AE onset date is missing the day only, it will be set to:
 - The first day of the month when the AE occurred, if month/year of the AE onset date is different than the month/year of the first administration of study treatment date.
 - The day of the first study treatment administration, if the month/year of the AE onset date is the same as the month/year of the first study treatment administration but the month/year of the AE resolution date is different.
 - The earliest between the day of the first study treatment administration date and day of AE resolution date, if month/year of the AE onset are the same as both the month/year of the first study drug administration and the AE resolution date.
- If the AE onset date is missing both day and month, it will be set to the earliest of:
 - January 1 of the year of onset, as long as this date is on or after the first study drug administration.
 - Month and day of the first study treatment administration, if this date is in the same year of AE onset date.
 - December 31 if the AE onset date year is prior to the year of the first study drug administration.
 - The AE resolution date.
- Completely missing onset dates will not be imputed.

Partial AE resolution dates not marked as ongoing will be imputed as follows:

- If the resolution date of an AE is missing the day only, it will be set to the earliest of the last day of that month or the day of the date of death, if the participant died in that month.
- If the resolution date of an AE is missing both day and month, it will be set to the earliest of December 31 of that year or the day and month of the date of death, if the participant died in that year.
- Completely missing resolution dates will not be imputed.

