5.1.1. Analysis Phase

The analysis phases are defined in [Table 3](#) below.

Table 3: Analysis Phases Start and End Dates

Analysis Phase	Start date	End date
Screening	The date of signing the informed consent	1 day before the first study agent intake (excluding PegIFN- α 2a)
Treatment Period 1	Date of first study agent intake (excluding PegIFN- α 2a)	For participants who receive PegIFN-α2a: Min [Date of first PegIFN- α 2a intake - 1 day, cut-off date ^b]
		For participants who do not receive PegIFN-α2a: Date of Week 12 study agent intake - 1 day
		For participants who discontinue treatment before Week 12: Max [last intake date of any study agent, study agent discontinuation date, early study withdrawal visit date] + 5 days ^a or cut-off date ^b , whichever occurs first
Treatment Period 2	For participants who receive PegIFN-α2a: Date of first PegIFN- α 2a intake	For participants who did not withdraw from the study prior to the projected/actual Week 24 visit date: Max [last intake date of any study agent, study agent discontinuation date, projected/actual Week 24 visit date] + 5 days ^a or cut-off date ^b , whichever occurs first
	For participants who do not receive PegIFN-α2a: Date of Week 12 study agent intake	
	Otherwise: missing	
Follow-up	Participants who did not withdraw informed consent during treatment period 1 or 2: Max [End date of Treatment Period 1, End date of the Treatment Period 2] + 1 day	Max [study discontinuation date, study completion date] or cut-off date ^b , whichever occurs first
	Otherwise: missing	Otherwise: missing

^a Addition of 5 days is only applicable for Adverse Events and Concomitant Medications.

^b Cutoff dates will be defined to match the prespecified timepoints for DRC safety monitoring, interim analyses, the primary and final analyses, respectively.

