5.6. Safety Analyses

All safety analyses will be performed using the safety analysis set. All assessments will be presented by analysis phase (for treatment period 1, for treatment period 2 and FU phase) and overall. All summaries will be descriptive.

Safety and tolerability will be assessed by evaluating treatment emergent-adverse events (TEAEs), physical examinations, ophthalmic examinations, vital signs measurements, clinical laboratory tests (including hematology, blood biochemistry, blood coagulation, and urinalysis), and ECGs.

Continuous parameters will be summarized using the following statistics: number of observations, mean, standard deviation (SD), standard error (SE), minimum, median and maximum, unless specified otherwise. Frequencies and percentages will be used for summarizing categorical data.

Some analysis will be performed by group, as defined in Section 5.1.10.

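### Adverse events with a missing onset day in the month PegIFN starts are almost always tabulated in Treatment Period 1, because the imputation rule is tied only to the first study treatment

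*SAP*

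**What the plan says.** SAP 5.1.8.1 gives the rules for partial AE onset dates. If only the day is missing, the default is "The first day of the month when the AE occurred, if month/year of the AE onset date is different than the month/year of the first" dose. The exception applies in the month of first dosing, where the imputed date is "The day of the first study treatment administration, if the month/year of the AE onset date is the same as the month/year" of first study treatment, or the resolution date if that is earlier in the same month. If day and month are both missing, the candidate dates include "Month and day of the first study treatment administration, if this date is in the same year of AE onset date". Every exception refers to first study treatment or first study drug. None refers to PegIFN or to a later phase boundary.

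SAP 5.1.1 (Table 3) ends Treatment Period 1, for participants who receive PegIFN, at "Date of first PegIFN- α 2a intake - 1 day" (or the data cut-off, if sooner). SAP 5.1.3 adds that "Day 85 is the target day for the first administration of PegIFN- α 2a".

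SAP 5.6 then states: "All assessments will be presented by analysis phase (for treatment period 1, for treatment period 2 and FU phase) and overall". Protocol 9.4.3 likewise calls for safety by study period. SAP 5.1.8 reserves the original, unimputed dates for listings, so the phase tables use the imputed ones.

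**The concern.** The SAP recognises that an ambiguous AE in the month of first dosing should not be dated before the drug, and guards against it. The same ambiguity arises about 12 weeks later when PegIFN is added, and there the default works the other way. An event that began on PegIFN but lacks its onset day is dated to the 1st of the month and tabulated in the period before PegIFN was given.

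The other partial-date provision, in SAP 5.6.2, does not repair this. It decides whether an event is treatment-emergent relative to first study intervention, not whether it belongs to Period 1 or Period 2.

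The study has one arm, so the phase tables are where a reader will look for a change in the AE profile once PegIFN is added. An event judged related to PegIFN could also appear in Period 1, before any PegIFN had been given.

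**Working it through.** The plan states no figure on this point: no AE rate, no partial-date rate and no projected phase counts. The check therefore applies the stated rules to every possible date.

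**Inputs from the SAP.** Day-missing onset rules (5.1.8.1). Period 1 ends the day before first PegIFN, and Period 2 for AEs runs to the Week 24 date plus 5 days (5.1.1, Table 3). PegIFN target Day 85 and Week 24 target Day 169 (5.1.3). Period 1 is then Days 1 to 84 (84 days), and Period 2 for AEs is Days 85 to 174 (90 days).

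**Step 1: one worked case.** First dose 10 June, PegIFN 2 September.
- AE on 20 September, day missing: imputed 1 September, so Period 1. Wrong.
- AE on 20 October: imputed 1 October, so Period 2. Correct.
- AE on 20 November: imputed 1 November, so Period 2. Correct.

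Only the PegIFN start month is affected at this boundary. In later months of Period 2, the 1st already falls after PegIFN.

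**Step 2: the start month by hand.** Take a 30-day month with PegIFN starting on day s, each s from 1 to 30 equally likely, and a flat AE rate.
- On-PegIFN days in that month: sum of (31 − s) = 465 out of 30 × 30 = 900, or 51.7%.
- Days the rule assigns to Period 2: only s = 1, so 30/900 = 3.3%. The other 96.7% go to Period 1.
- True on-PegIFN days sent to Period 1: (465 − 30)/465 = 93.5%.
- Average on-PegIFN days moved per participant: 435/30 = 14.5. As a share of Period 2: 14.5/90 = 16%.

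**Step 3: full enumeration.** The rules were applied to 730 first-dose dates (2021 and 2022), PegIFN on Day 85, and every onset day through follow-up. The AE-rate patterns are assumptions: flat; three or five times higher in Period 2; and front-loaded (six times in the first 28 days of PegIFN, twice for the other 62). First dose and first PegIFN never shared a calendar month. In the start month, 95% to 97% of day-missing AEs went to Period 1, as did about 94% of those that truly began on or after PegIFN.

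The first-of-month rule also acts at the end of Period 2, where it pulls early follow-up AEs back into Period 2. Hence net Period 2 assigned/true = 1 − (share lost to Period 1) + (share gained from follow-up).

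| Assumed AE rate | Period 2 AEs sent to Period 1 | Follow-up AEs pulled in, as share of true Period 2 | Period 2 assigned/true | Period 1 assigned/true |
|---|---|---|---|---|
| Flat | 16.4% | 16.4% | 1.00 | 1.18 |
| 3× in Period 2 | 16.4% | 5.5% | 0.89 | 1.53 |
| 5× in Period 2 | 16.4% | 3.3% | 0.87 | 1.88 |
| Front-loaded | 30.2% | 5.0% | 0.75 | 2.05 |

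The last column is 1 + (AE weight moved)/84. Flat: 1 + 0.164 × 90/84 = 1.18. Front-loaded: the Period 2 weight is 28 × 6 + 62 × 2 = 292, so 1 + 0.302 × 292/84 = 2.05. With the 3× pattern, shifting the PegIFN start by −2 to +7 days gives 16% to 18% moved.

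**Step 4: scale.** These ratios concern day-missing AEs only. If 2% to 10% of onsets lack a day (an assumption), the share of all Period 2 AEs moved is between 0.02 × 0.16 = 0.3% and 0.10 × 0.30 = 3%.

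**Step 5: effect of a PegIFN-start rule.** Setting every day-missing onset of that month to the PegIFN date reduces the loss to Period 1 to zero. It also moves that month's true Period 1 AEs into Period 2. Period 2 assigned/true becomes 1.33 (flat), 1.11 (3×), 1.07 (5×) or 1.10 (front-loaded), and Period 1 keeps about 82% of its day-missing AEs. These figures make no use of resolution dates or other recorded information, which would reduce the overcorrection.

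**The case against.** The strongest reply is that little is lost. AEs are also reported overall and by relationship to each agent, and unimputed dates appear in listings; none of these depends on the Period 1/Period 2 split. All safety summaries are descriptive, and no test between periods is planned. The Schedule of Activities reviews AEs at every visit, including Weeks 12, 14 and 16. Sites in Japan see participants twice in the first PegIFN week and weekly to Week 23. Partial dates should be few. All of this stands, and it keeps the point minor.

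It also stands that a PegIFN-start rule replaces one error with another. At a flat rate, about 48% of the start month's AEs truly precede PegIFN. The case for the rule is that its error is conservative for PegIFN safety and follows the convention the SAP already uses for first dose.

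Several stronger readings are tempting, but the documents do not support them:
- A reader might infer that nearly all partially dated AEs land before PegIFN. That is true only of the start month; 70% to 84% of day-missing Period 2 AEs stay in Period 2.
- A reader might infer that PegIFN harms are necessarily undercounted in Period 2. At a flat rate the two boundaries cancel, so a net deficit needs an assumed PegIFN effect.
- A reader might take Period 1 versus Period 2 as the design's main safety contrast. The safety objective covers the whole study, and the SAP only tabulates the phases.
- A reader might expect mood events to be especially prone to partial dates. Nothing in the documents says so, and the protocol requires close neuropsychiatric monitoring during PegIFN.

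**Conclusion.** The gap is real and follows directly from SAP 5.1.8.1 and Table 3. A day-missing AE in the PegIFN start month is tabulated in Period 1 unless PegIFN began on the 1st, even when the event began on PegIFN.

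Among day-missing AEs, about 16% (flat or uniformly raised rate) to 30% (front-loaded) of Period 2 events are misplaced. Period 1 is inflated under every pattern tried, and the net Period 2 count runs from unchanged to about 25% low. The sizes rest on the assumed AE-rate patterns and on PegIFN starting near Day 85; the direction of the error at this boundary does not. Events are misplaced in the phase tables and not lost from the study's totals. The effect on all AEs cannot be sized from the documents and is probably small. This is a cheap improvement to the SAP.

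**What to change.** Add to SAP 5.1.8.1: if only the day is missing and the onset month and year equal those of first PegIFN, set onset to the first PegIFN date, or to the resolution date if earlier, unless other recorded information shows onset before PegIFN. State also that day-missing onsets in the month Period 2 ends remain in Period 2, as the current rule already gives, so that both later boundaries are explicit.

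Leave year-only dates as they are. The current rule does send about 88% of year-only onsets that truly belong to Period 2 into Period 1. But a PegIFN rule for them would date true Period 1 events to the PegIFN start, and such dates should be very rare under this visit schedule.

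The cost is a bullet or two in the SAP and a line of programming. No data collection or participant management changes. The downside, to be disclosed with the tables, is that some AEs from that month that began before PegIFN are counted in Period 2, which stands at about 1.1 to 1.3 times its true day-missing count before resolution dates are used.
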